9.5.2 Concomitant medication

Concomitant medication will be coded using the WHO drug dictionary (Version March 2017 Enhanced Dictionary B2 Format. Concomitant medication will be listed.

9.5.3 Clinical laboratory parameters

Clinical chemistry, hematology and urinalysis data outside the reference ranges will be listed.

Values for any clinical chemistry, hematology and urinalysis values outside the reference ranges will be flagged on the individual subject data listings.

9.5.4 Hepatic Monitoring

If a subject experiences elevated alanine aminotransferase (ALT) $\geq 3 \times$ upper limit of normal (ULN), alkaline phosphatase (ALP) $\geq 2 \times$ ULN, or elevated total bilirubin (TBL) $\geq 2 \times$ ULN, liver tests will be performed to confirm the abnormality.

The subjects' liver disease history and associated person liver disease history data will be listed. Any concomitant medication of acetaminophen/paracetamol will be listed. Results from a magnetic resonance elastography (MRE) scan and biopsy assessment will be listed, if performed.

Hepatic risk factor assessment data will be listed by study phase. Liver related signs and symptoms data will be summarized by study phase and treatment, and listed, if available.

All hepatic chemistry, hematology, coagulation, and serology data will be summarized by study phase, parameter, and treatment, and listed. Values outside the reference ranges will be flagged on the individual subject data listings.

9.5.5 Vital signs

Vital signs data will be summarized by study phase and treatment together with changes from baseline, where baseline is defined as Day 1 predose for each study phase separately. Figures of mean vital signs and mean changes from baseline profiles by treatment will be presented by study phase and treatment. Furthermore, values for individual subjects will be listed by study phase.

Changes from baseline (predose) will be calculated for vitals signs.

9.5.6 Electrocardiogram (ECG)

For each subject, ECGs will be performed for safety purposes only, and will not be reported.

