Subjects who complete all 5 periods of the Treatment Phase will comprise the completers population; this will be the population used for analyzing the Drug Effects VAS Battery. Descriptive statistics for continuous variables will include mean, standard error, minimum, first quartile, median, third quartile, and maximum. Descriptive statistics for categorical variables include count and percent.

Descriptive statistics for the Drug Liking VAS will be reported for each treatment and for each paired difference among treatments. A linear mixed-effects model, which includes period, sequence, and treatment as fixed effects, and subject as a random effect will be used to evaluate the hypothesis tests of primary interest at the peak of drug response effects (E_{max}) at a significance level of 0.05 (1-sided).

Descriptive statistics for other measures in the Drug Effects and Drug Similarity VAS Battery, adverse events, safety laboratory parameters, vital signs, Columbia-Suicide Severity Rating Scale (C-SSRS), ECG, and pharmacokinetic parameters will be reported by treatment.

2. Schedule of Activities

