10.2. Populations for Analyses

Subjects who complete all 5 periods of the Treatment Phase will comprise the Completers population; this will be the population used for analyzing the Drug Effects VAS Battery. Pharmacokinetic/Pharmacodynamic (PK/PD) analyses will be conducted on data from all subjects who receive at least 1 dose of lasmiditan or alprazolam and have evaluable PK. All subjects who take at least 1 dose of the investigational product will comprise the safety population; this will be the population used for all analyses except the Drug Effects VAS Battery analyses and PK/PD analyses.

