10.3.1.2. Statistical Evaluation of Safety

Safety parameters that will be assessed include safety laboratory parameters, vital signs, C-SSRS, and ECG parameters. The parameters will be listed and summarized by treatment, using standard descriptive statistics. Additional analyses will be performed, if warranted, upon review of the data.

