3. INTRODUCTION

This SAP has been developed after review of the Clinical Study Protocol (final version dated 24 July 2017 and Protocol Amendment (c) (final version dated 06 September 2017).

This SAP describes the planned analysis of the safety, tolerability, pharmacokinetic (PK) and pharmacodynamic (PD) data from this study. A detailed description of the planned TFLs to be presented in the clinical study report (CSR) is provided in the accompanying TFL shell document.

The intent of this document is to provide guidance for the statistical and PK analyses of data. In general, the analyses are based on information from the protocol, unless they have been modified by agreement between Eli Lilly and Company and Covance Early Clinical (EC) Biometrics. A limited amount of information concerning this study (e.g., objectives, study design) is given to help the reader's interpretation. This SAP must be signed off prior to first subject administration for this study. When the SAP and TFL shells are agreed upon and finalized, they will serve as the template for this study's CSR.

This SAP supersedes the statistical considerations identified in the protocol; where considerations are substantially different, they will be so identified. If additional analyses are required to supplement the planned analyses described in this SAP, they may be performed and will be identified in the CSR. Any substantial deviations from this SAP will be agreed upon between Eli Lilly and Company and Covance EC Biometrics and identified in the CSR. Any minor deviations from the TFLs may not be documented in the CSR.

This SAP is written with consideration of the recommendations outlined in the International Conference on Harmonisation (ICH) E9 Guideline entitled Guidance for Industry: Statistical Principles for Clinical Trials¹ and the ICH E3 Guideline entitled Guidance for Industry: Structure and Content of Clinical Study Reports².

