8. DEFINITION OF ANALYSIS POPULATIONS

8.1 Populations

The “Safety” population will consist of all subjects who received at least one dose of study drug (lasmiditan, alprazolam, or placebo). This will be the population used for all analyses except the Drug Effects VAS battery analyses and PK/PD analyses.

The “Pharmacodynamic” population will consist of all subjects who received at least one dose of lasmiditan, alprazolam or placebo and have evaluable PD data. This will be evaluated for the Qualification Phase and Treatment Phase separately. Subjects may be excluded from the PD summary statistics and statistical analysis if a subject has an AE of vomiting that occurs at or before 2 times median time of maximum observed drug concentration (t_{max}).

The “Pharmacokinetic” population will consist of all subjects who received at least one dose of lasmiditan or alprazolam and have evaluable PK data in the Treatment Phase. The PK population is applicable to the Treatment Phase only. Subjects may be excluded from the PK summary statistics and statistical analysis if a subject has an AE of vomiting that occurs at or before 2 times median t_{max} .

For the statistical analysis of the Drug Effects VAS Battery in the Treatment Phase, the analysis will be performed only subjects who complete all 5 periods.

All protocol deviations that occur during the study will be considered for their severity/impact and will be taken into consideration when subjects are assigned to analysis populations.

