9. STATISTICAL METHODOLOGY

9.1 General

Data listings will be provided for all data that is databased. Summary statistics and statistical analysis will only be presented for data where detailed in this SAP. For continuous data, summary statistics will include the arithmetic mean, arithmetic standard deviation (SD), standard error (SE), first quartile, median, third quartile, min, max and N; for log-normal data (e.g. the PK parameters: area under the concentration versus time curve [AUCs] and maximum observed drug concentration [C_{max}]) the geometric mean and geometric coefficient of variation (CV%) will also be presented. For categorical data, frequency count and percentages will be presented. Data listings will be provided for all subjects up to the point of withdrawal, with any subjects excluded from the relevant population highlighted. Summary statistics and statistical analyses will generally only be performed for subjects included in the relevant analysis population. For the calculation of summary statistics and statistical analysis, unrounded data will be used.

Mean change from baseline is the mean of all individual subjects' change from baseline values. Each individual change from baseline will be calculated by subtracting the individual subject's baseline value from the value at the timepoint. The individual subject's change from baseline values will be used to calculate the mean change from baseline using a SAS procedure such as Proc Univariate.

Data analysis will be performed using SAS[®] Version 9.3 or greater.

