11. CHANGES FROM THE PROTOCOL SPECIFIED STATISTICAL ANALYSES

There were no changes from the protocol specified statistical analyses.

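### The SAP drops the by-treatment ECG summary that the protocol promises and declares no change; its AE phase rule also attributes some worsened events to the wrong phase

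*SAP*

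**What the plan says.** **ECG, protocol.** Section 10.3.1.2 includes ECG among the safety parameters: "vital signs, C-SSRS, and ECG parameters. The parameters will be listed and summarized by treatment". The Statistical Analysis part of the synopsis says the same of descriptive statistics: "ECG, and pharmacokinetic parameters will be reported by treatment".

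**ECG, SAP.** Section 9.5.6 reads: "ECGs will be performed for safety purposes only, and will not be reported".

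**How the two documents relate.** SAP 3 gives the SAP precedence over the protocol's statistical text, with the condition that "where considerations are substantially different, they will be so identified". SAP 11 then states: "There were no changes from the protocol specified statistical analyses". SAP 9.1 promises listings of whatever is in the database, and adds: "Summary statistics and statistical analysis will only be presented for data where detailed in this SAP".

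**Population.** Protocol 10.2: "All subjects who take at least 1 dose of the investigational product will comprise the safety population". SAP 8.1 says of its Safety population: "This will be the population used for all analyses except the Drug Effects VAS battery analyses and PK/PD analyses".

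**Adverse events.** SAP 9.5.1 treats an event as treatment-emergent if it arises after dosing, or if it was there before dosing and then worsens. The TEAE definition in protocol Appendix 1 likewise covers worsening. SAP 9.5.1 also says that events starting before the Treatment Phase appear in the Qualification summaries alone, and that events carried over from Qualification are flagged in Treatment Phase listings but left out of the tables. Summary tables use the worst severity recorded.

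**C-SSRS.** Protocol 10.3.1.2 promises a summary by treatment; SAP 9.5.7 provides individual listings only.

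**The concern.** The two documents cannot both be followed on ECG. The SAP takes precedence, so in practice the protocol commitment lapses. Someone who relies on section 11 to learn what changed would conclude that nothing had.

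What is lost is this study's descriptive ECG data by dose, including 400 mg, which protocol 5.5.1 calls the highest oral dose tested in the programme to date. Protocol 9.4.4 itself names QTc change from baseline as an example of a clinically significant finding.

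The adverse-event point matters because TEAE profiles are the safety endpoint in protocol section 4. A table that assigns a worsening to a Qualification treatment, when it followed a Treatment Phase dose, misstates the profile of both treatments.

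**Working it through.** The plan states no figure to reproduce here. The check is a comparison of the texts, plus a count for scale.

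**1. Can any other SAP text supply the ECG summary?**
- SAP 9.1 limits summaries to data for which the SAP specifies them. No SAP section specifies an ECG summary, so none is produced.
- SAP 9.1 also promises listings of all databased data. If ECG values are databased, this conflicts with 9.5.6 on listings. Whichever sentence prevails, there is still no summary by treatment.
- SAP 9.5.8 covers only safety assessments that section 9.5 does not address. ECG is addressed, so 9.5.8 does not reach it.
- Protocol 9.4.4 sends clinically relevant ECG findings to adverse-event reporting. That puts findings, not interval values by dose, into the tables.
- An outdated protocol is not the explanation: SAP 3 says the SAP was written after review of Amendment (c).

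**2. Scale.** The Treatment Phase schedule (protocol 2.2) has ECGs on Day -1 and at 0, 2, 4 and 24 h in each of 5 periods, so 3 per period are post-dose. Protocol 10.1 plans about 60 randomized subjects and about 50 completers. The Qualification schedule (protocol 2.1) has ECGs only at screening and Day -1, so it adds no post-dose readings.

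| Quantity | 50 completers only | All 60 complete |
|---|---|---|
| Post-dose, all treatments | 3 × 5 × 50 = 750 | 3 × 5 × 60 = 900 |
| Post-dose, per treatment | 3 × 50 = 150 | 3 × 60 = 180 |
| Post-dose, three lasmiditan doses | 3 × 150 = 450 | 3 × 180 = 540 |

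The safety analyses use all dosed subjects. The left column therefore ignores ECGs from subjects who drop out, and the right column assumes that none do. Replacements beyond 60 are not counted.

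**3. The adverse-event rule, traced through an illustration.** Suppose a mild event starts after the Qualification placebo dose, is still ongoing, and becomes severe after a 400-mg lasmiditan dose.
- By the definition in 9.5.1, worsening after a dose is treatment-emergent.
- By the phase rule, the event started before the Treatment Phase, so it goes to the Qualification summaries alone.
- By the worst-severity rule, it is tabulated there as severe, under placebo.
- By the exclusion rule, it is absent from the Treatment Phase table for 400 mg.

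If the site instead enters the worsening as a new event with a Treatment Phase start date, it is tabulated under 400 mg. The documents do not say which recording rule applies.

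**4. C-SSRS.** In the Treatment Phase schedule it is taken on Day -1 of Period 1, at discontinuation or early termination, and at follow-up. Periods 2 to 5 are added only if the subject was discharged between periods.

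**The case against.** The strongest reply on ECG is that SAP 3 lets the sponsor and its contractor agree changes and gives the SAP precedence, so dropping ECG output is permitted and 9.5.6 says openly that it is dropped. ECG is not an endpoint, clinically relevant findings still become adverse events, and a thorough QT study exists (protocol 5.5.1). All of that stands, and it limits the severity. It does not make section 11 correct: the SAP's own condition for departing from the protocol is that the departure be identified, and it is not. A declaration in section 11 would cure the inconsistency, although it would not deliver the promised output.

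A reader might infer that ECG information can reach the report only through adverse events. The documents do not support that, because SAP 9.1 also promises listings of databased data and the TFL shells are not among the documents reviewed. The supported statement is narrower: there is no summary by treatment.

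A reader might also infer that a worsened Qualification event disappears from every by-treatment table. It does not. The Qualification tables are themselves by treatment (SAP 6), and the event is in them at its worst grade. The fault is attribution between phases.

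For C-SSRS, the sparse schedule makes a summary by treatment of little use in a crossover, so a listing alone may be reasonable. Only the declaration is missing.

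It is tempting to add routine laboratory data, for which SAP 9.5.3 gives only listings. But SAP 9.5.4 summarizes hepatic chemistry and hematology by treatment, and it is unclear whether that covers routine samples. No departure can be asserted for laboratory data from this text.

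**Conclusion.** The ECG contradiction is direct, and no other text resolves it. The protocol promises listings and summaries by treatment, the SAP withholds them, and SAP 11 wrongly reports no change. On the planned numbers, about 750 to 900 post-dose ECGs go unsummarized, 450 to 540 of them on lasmiditan. This assumes that the schedule is followed in every period and that between 50 and 60 subjects contribute all five. These are counts of data and imply nothing about any ECG effect. Given the thorough QT study, it would also be wrong to infer that the programme loses its only QT evidence.

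The adverse-event fault is real but smaller. It applies only where worsening is recorded as a severity change of the same event. The number of such events is unknown and probably small, and they stay flagged in listings. The C-SSRS departure is minor.

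The primary Drug Liking analysis is untouched. The sponsor should correct these points. Confidence is high on the ECG contradiction; the practical effect of the adverse-event rule depends on a recording convention that the documents do not give.

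**What to change.** 1. **SAP 9.5.6.** Replace the text with a listing and a descriptive summary of ECG parameters by treatment and time point, on the Safety population. If change is shown, take the 0 h ECG of the same period as baseline; the schedule has one in every period. If ECG reporting is to stay out, declare that in section 11 with the sponsor's reason, and reconcile 9.5.6 with the listings sentence in 9.1.
2. **SAP 9.5.1.** Add that an event ongoing from Qualification which increases in severity after a Treatment Phase dose is counted as a TEAE under that period's treatment. Limit its Qualification entry to the severity reached before Treatment Phase dosing.
3. **SAP 11.** Declare that C-SSRS is listed only, with the reason, and remove the statement that nothing changed.

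**Cost.** One set of ECG tables and listings, one programming rule for adverse events, and a corrected section 11. The ECGs are already scheduled and recorded digitally (protocol 9.4.4), so no procedure is added for subjects. The documents do not show whether numeric ECG values are captured in the database; if they are not, they must be added or the omission declared. SAP 3 requires sign-off before the first subject is dosed, so the changes belong before then.

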9.5.7 Columbia-Suicide Severity rating Scale (C-SSRS)

The Columbia Suicide Severity Rating Scale will be listed for individual subjects.

9.5.8 Other assessments

All other safety assessments not detailed in this section will be listed but not summarized or statistically analyzed.

9.5.9 Safety and Tolerability Statistical Methodology

No inferential statistical analyses are planned.

10. INTERIM ANALYSES

No interim statistical analyses are planned.

11. CHANGES FROM THE PROTOCOL SPECIFIED STATISTICAL ANALYSES

There were no changes from the protocol specified statistical analyses.

13. DATA PRESENTATION

13.1 Derived Parameters

Individual derived parameters (e.g. PK parameters) and appropriate summary statistics will be reported to three significant figures. Observed concentration data, e.g. C_{max} , should be reported as received. Observed time data, e.g. t_{max} , should be reported as received. N and percentage values should be reported as whole numbers. Median values should be treated as an observed parameter and reported to the same number of decimal places as minimum and maximum values.

13.2 Missing Data

Missing data will not be displayed in listings.

